5.1.2 Expansion Phase

Once the MTD is established, an additional cohort of patients will initially be treated with pazopanib alone, and tumor biopsies will be obtained to assess target inhibition, as outlined below. Tumor biopsies will be mandatory during the expansion phase of the study. Biopsies will be obtained at the time points outlined below. Depending on the results obtained from the tumor biopsies in the first few patients, the timing of the biopsy can be adjusted, but the number of tumor biopsies and the procedure will not change. Any change in the timing of the tumor biopsy will be discussed with the patient prior to obtaining informed consent.

The cohort and dosing regimens after establishment of the MTD are described below. When administered as a single agent during the expansion phase, the dose of pazopanib will correspond to the dose determined for the combination MTD if the MTD is determined at dose level 5 (ARQ 197 360 mg BID/pazopanib 800 mg QD) or 6 (ARQ 197 360 mg BID/pazopanib 600 mg QD). Otherwise, the dose of pazopanib will be determined after discussion with CTEP. Once the MTD is established, the data will be discussed with CTEP prior to proceeding with accrual for the expansion phase.

Cohort A (12 patients): Pazopanib will be given once daily as single agent from cycle 1 day 1 to day 7. Tumor biopsy will be done before drug administration on study (baseline) and on cycle 1 day 8, 8-12 hours after pazopanib administration. **After** the tumor biopsy, patients will start to receive ARQ 197 in addition to pazopanib at the combination MTD.

Twelve evaluable patients with both pre- and post-treatment biopsies will be treated initially in Cohort A. Mean increases in MET and pMET in these 12 patients will be measured to assess whether or not they are statistically significant.

For the purposes of final analysis of the expansion phase, only patients with paired tumor biopsies will be considered evaluable. Patients with fewer than the 2 required biopsies will not be considered evaluable for the expansion phase and will need to be replaced in the accrual scheme of the expansion phase. If a patient has a dose-limiting toxicity (DLT) with the single lead-in agent pazopanib in the expansion cohort, the patient will be taken off treatment.

5.2 Definition of Dose-Limiting Toxicity

Dose-limiting toxicity (DLT) is defined as an adverse event that is related (possibly, probably, or definitely) to administration of study drugs and fulfills one of the following criteria:

5.2.1 Grade \geq 3 Non-Hematological Toxicity

Grade \geq 3 non-hematological toxicity felt to be related to study medications will be considered dose-limiting with the following clarifications:

- 5.2.1.1 Diarrhea Grade 3 will only be considered dose-limiting if it is refractory to treatment as outlined in [Section 5.3.2](#), Supportive Care Guidelines, and unable to be corrected to Grade 2 or less within 24 hours. Bloody or Grade 4 diarrhea will be dose-limiting.
- 5.2.1.2 Nausea and vomiting Grade 3 will only be considered dose-limiting if it is refractory to anti-emetic therapy and unable to be corrected to Grade 1 or less within 24 hours ([Section 5.3.1](#)).
- 5.2.1.3 Rise in creatinine to Grade 3, not corrected to Grade 1 or less within 48 hours with IV fluids will be considered dose-limiting. All Grade 4 rises in creatinine will be dose limiting.

5.2.1.4 Grade ≥ 3 metabolic toxicities unable to be corrected to Grade 2 or less within 48 hours (such as glucose changes, hypocalcemia or hypercalcemia, hypomagnesemia or hypermagnesemia, hyperuricemia, hypophosphatemia, and hyponatremia) will be considered dose limiting. For hypokalemia or hyperkalemia, grade ≥ 2 toxicities unable to be corrected to grade 1 or less within 48 hours will be considered dose limiting. Grade 4 metabolic toxicities that are symptomatic will be considered dose-limiting regardless of duration or ability to correct.

5.2.1.5 QTc prolongation to ≥ 500 msec on at least two separate EKGs (refer to [Section 5.3](#)) will be dose limiting.

5.2.1.6 AST/ALT > 8 X ULN or AST/ALT > 3 X ULN and concurrent bilirubin elevation > 2 X ULN will be dose limiting.

5.2.1.7 Grade ≥ 3 bleeding in any sites or grade ≥ 2 pulmonary bleeding will be dose limiting.

5.2.1.8 Grade 4 venous thrombosis, pulmonary embolism, or any grade of arterial thrombosis will be dose limiting.

5.2.2 Grade 4 thrombocytopenia.

5.2.3 Grade 4 neutropenia ≥ 3 days or febrile neutropenia.

5.2.4 Any degree of anemia, leucopenia in the absence of grade 4 neutropenia ≥ 3 days, or lymphopenia will not be considered dose limiting.

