5.3.2 Diarrhea

If diarrhea develops and does not have an identifiable cause other than study drug administration, anti-diarrheals such as Lomotil (diphenoxylate HCl 2.5 mg + atropine sulfate 0.025 mg/tablet) dosed according to package insert or loperamide 4 mg po after the first unformed stool with 2 mg po with every 2 hours (4 mg every 4 hours while asleep), till resolution of episode of at least 12 hours (no more than 16 mg of loperamide

during a 24-hour period). This regimen can be repeated for each diarrheal episode. Diarrhea will be considered refractory if it does not resolve within 24 hours to \leq Grade 2 with the above regimen (maximum of 16 mg of loperamide in a 24-hour period). If the patient develops blood or mucus in the stool, dehydration, or hemodynamic instability, or fever along with the diarrhea, anti-diarrheals will be discontinued and the patient will be treated with IV fluids and antibiotics as medically indicated.

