6.1 Dose Reduction

6.1.1 Doses will be modified for grade 3 or greater non-hematologic toxicity with the following clarifications:

- Doses will not be modified for electrolyte abnormalities, unless these are not correctable within 48 hours, or for alopecia.
- Dose of study drugs will not be reduced for nausea, vomiting, or diarrhea unless these are considered refractory as defined in [Section 5.3](#).
- Dose reductions may occur to a single compound, independent of the other compound. Doses of ARQ 197 will not be reduced for any grade hypertension or proteinuria.
- For uncontrolled hypertension (as defined in [Section 6.1.5](#)), only the dose of pazopanib will be reduced to the next lower dose level.
- For proteinuria, only the dose of pazopanib will be reduced to the next lower dose level ([Section 6.1.6](#)).

6.1.2 Grade 2 drug-related toxicity: No changes will be made to the dose of either study drug for Grade 2 toxicities, and therapy will not be interrupted, except as otherwise noted (e.g., hypokalemia or hyperkalemia as described above, Grade 2 hemorrhage or thrombosis as described in [Section 6.1.10](#)). However, for persistent symptomatic skin rash or hand foot syndrome limiting instrumental activities of daily living that do not improve to grade 1 or less within 2 weeks with optimal management, doses of both pazopanib and ARQ 197 will be held until toxicities have resolved to \leq Grade 1 prior to re-starting study treatment. Therapy will be re-initiated at the next lower dose level.

6.1.3 Grade 3 drug-related neutropenia and/or thrombocytopenia: Doses of both pazopanib and ARQ 197 will be held until toxicities have resolved to \leq Grade 2 prior to re-starting study treatment. Therapy will be re-initiated at the same dose level at the first occurrence of either event. In the case of second occurrence of

either event, therapy will be re-initiated at the next lower dose level. Therapy will not be interrupted or doses modified for any grade lymphopenia, anemia, or leucopenia in the absence of grade 3 or 4 neutropenia.

6.1.4 Grade 4 drug-related neutropenia ≥ 3 days and/or thrombocytopenia: Doses of both pazopanib and ARQ 197 will be held until toxicities have resolved to \leq Grade 2 prior to re-starting study treatment. Therapy will be re-initiated at the next lower dose level.

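### Section 6.1.1 forbids a lower dose after a narrow set of quickly corrected Grade 4 DLTs, leaving only the same dose or stopping

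*Combined protocol and SAP*

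**What the plan says.** Section 5.2.1 makes related non-hematological toxicity of Grade 3 or higher dose-limiting, subject to clarifications.

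- Diarrhea (5.2.1.1): Grade 3 counts only if refractory, but "Bloody or Grade 4 diarrhea will be dose-limiting".
- Nausea and vomiting (5.2.1.2): "Nausea and vomiting Grade 3 will only be considered dose-limiting if it is refractory to anti-emetic therapy". Grade 4 is not mentioned.
- Creatinine (5.2.1.3): Grade 3 counts only if not corrected within 48 hours, but "All Grade 4 rises in creatinine will be dose limiting".
- Metabolic toxicity (5.2.1.4): events not corrected within 48 hours count, and "Grade 4 metabolic toxicities that are symptomatic will be considered dose-limiting regardless of duration or ability to correct".

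Section 6.1.1 sets the individual patient's dose: "Doses will be modified for grade 3 or greater non-hematologic toxicity with the following clarifications". Two of its clarifications matter here: "Doses will not be modified for electrolyte abnormalities, unless these are not correctable within 48 hours" and "Dose of study drugs will not be reduced for nausea, vomiting, or diarrhea unless these are considered refractory". Refractory is defined in 5.3.1 (vomiting not down to Grade 1 within 24 hours on at least two antiemetics) and in 5.3.2 (diarrhea not down to Grade 2 within 24 hours on the stated regimen). Neither clarification makes an exception for Grade 4 events or for DLTs.

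**The concern.** At Grade 3 the two sections ask the same question: did the event resist treatment? At Grade 4, Section 5.2.1 stops asking it and Section 6.1.1 does not. A patient can therefore have an event that the protocol counts as dose-limiting and yet be barred from a lower dose. If the investigator thinks the patient should continue, but on less drug, the protocol does not allow it.

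This is a patient-safety point about one missing option. The affected categories are plausible for these drugs. Section 2.2 names vomiting and diarrhea as the most frequently reported serious adverse events across pazopanib studies, and mentions QT prolongation. Section 2.3.2 lists vomiting and dehydration among ARQ 197 serious events above 3%. Serious does not mean Grade 4, so none of this supplies a rate.

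**Working it through.** No sample size, power or error rate is involved, so the check is a comparison of rules. Every event below is taken as drug-related and quickly corrected.

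| Event and correction | 5.2.1 at Grade 3 | 5.2.1 at Grade 4 | 6.1.1 at Grade 4 |
|---|---|---|---|
| Diarrhea, to Grade 2 or less in 24 h on the 5.3.2 regimen | not a DLT | DLT (stated) | reduction forbidden |
| Vomiting, to Grade 1 or less in 24 h on at least two antiemetics | not a DLT | DLT (inferred from the general rule) | reduction forbidden |
| Symptomatic electrolyte toxicity, corrected in 48 h | not a DLT | DLT (stated) | modification forbidden |
| Creatinine rise, to Grade 1 or less in 48 h with IV fluids | not a DLT | DLT (stated) | dose modified by default |
| Symptomatic glucose or uric acid toxicity, corrected in 48 h | not a DLT | DLT (stated) | dose modified by default |

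The first three rows are the gap. The last two are close neighbours, equally correctable, for which a lower dose is available.

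**Is there an override elsewhere?**

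- Section 6 requires recovery before the next dose and allows at most 2 weeks of delay. That governs when treatment restarts, not the dose.
- Section 6 also requires an EKG, with action according to the result, for potassium, calcium, magnesium and phosphate disturbances. Section 5.2.1.4 names 10 metabolic toxicities. Removing glucose and uric acid leaves 10 − 2 = 8 electrolyte events. The EKG rule covers 7 of them, all but hyponatremia. It does not reach diarrhea or vomiting.
- Section 6 lets one drug be reduced alone when a toxicity calls for reduction. Section 6.1.1 says these events do not.
- Section 5.4 lets the investigator stop treatment.
- Section 5.1.2 takes a patient off treatment after a DLT on the pazopanib lead-in, so the gap does not arise there.
- Sections 6.1.2 to 6.1.10 contain no rule that lifts the bar.

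**Recurrence.** Section 6.1.3 requires a lower level at the second Grade 3 neutropenia or thrombocytopenia. The two bullets in 6.1.1 have no such rule, so repeated Grade 4 vomiting, each time controlled within 24 hours, never opens the way to a reduction.

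**Lower grades.** Persistent symptomatic Grade 2 rash or hand-foot syndrome (6.1.2) and Grade 2 non-pulmonary bleeding (6.1.10) do lead to a lower dose.

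**The case against.** The best defence is that the arrangement is deliberate. DLT status drives cohort escalation under 5.1.1, while 6.1.1 manages the individual, and nothing says that a DLT must lead to a lower dose. Grade 3 hypertension may resume at the same dose (Table 3), and febrile neutropenia with Grade 3 counts may restart at the same level the first time (6.1.3). With only two reductions allowed and no re-escalation, sparing quickly corrected events is coherent. This stands against making a reduction mandatory. It does not explain why a lower dose should be forbidden after a Grade 4 event.

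The defence also narrows the cases, and this stands:

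- Section 5.3.2 stops anti-diarrheals when there is blood, mucus, dehydration, hemodynamic instability or fever. Whether such diarrhea is refractory is then unclear, so it lies outside the point.
- If the symptom of an electrolyte event, or a complication, is itself a related Grade 3 or higher toxicity, the 6.1.1 default may modify the dose.
- The EKG rule leaves the resulting action open, which may give some latitude for the 7 electrolyte events it covers.
- The vomiting case is an inference, since 5.2.1.2 is silent on Grade 4.

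A reader might infer that 5.2.1 and 6.1.1 contradict each other. They do not: both can be obeyed at once, by counting the DLT and then holding the dose level or stopping.

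**Conclusion.** The gap is real but narrow. For uncomplicated Grade 4 diarrhea, Grade 4 vomiting and symptomatic Grade 4 electrolyte toxicity that respond within the stated windows, a patient outside the lead-in can only return to the same dose or leave treatment, however often the event recurs. The protocol states this as a prohibition; it is not missing detail.

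Its size cannot be given: the documents report no rate for these events in this combination, and they are likely uncommon. The conclusion assumes that the general Grade 3-or-higher rule makes Grade 4 vomiting a DLT, and that the 6.1.1 bullets mean what they say at Grade 4.

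Two stronger readings are not supported. One is that the MTD could be affected: escalation counts DLTs under 5.2.1 whatever 6.1.1 then does, and the planned analyses do not depend on it. The other is that these events ought to force a reduction: the protocol lets other DLTs resume at the same dose. This is a cheap improvement to dose management, not the repair of an error.

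**What to change.** Add to both the electrolyte bullet and the nausea, vomiting and diarrhea bullet of 6.1.1: *except that for an event meeting the DLT definition in 5.2.1, the dose of the drug(s) judged responsible may be reduced by one step at the investigator's discretion.* The clause should apply in any cycle; the first-cycle limit in 5.1.1 concerns DLT determination for escalation.

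Section 6 names no step below pazopanib 400 mg or below ARQ 197 120 mg BID. Use the single-drug steps found in Table 2: pazopanib 400 to 200 mg QD, and ARQ 197 120 mg BID to 120 mg QD. Moving a patient to level -1 or -2 as a whole does not work drug by drug. Level -1 leaves pazopanib at 400 mg, and level -2 lowers ARQ 197 no further than level -1. The ARQ 197 step is also needed at dose level 2.

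Keep the reduction optional, and leave 5.2.1, the escalation table and the lead-in rule in 5.1.2 as they are. The cost is a short protocol amendment with no extra patients or procedures. The downside falls on a patient who is reduced: one of the two allowed reductions is used and the dose is not raised again.

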5.3 General Concomitant Medication and Supportive Care Guidelines

All patients will be provided with the best available supportive care. All concurrent medications should be documented prior to initiation of treatment, and be periodically reviewed with the patient. Particular attention must be paid to medications which may prolong the QTc interval ([Appendix C](#)) and agents that interact with CYP450 isoenzymes ([Appendix B](#)).

QTc Prolongation:

Caution should be exercised when administering pazopanib to patients with a history of QTc interval prolongation, in patients taking anti-arrhythmics or other medications that may prolong the QTc interval, and those with relevant pre-existing cardiac disease. A list of medications that may cause QTc interval prolongation are listed in [Appendix C](#), and should be avoided by patients on this study. EKG will be performed as described in [Section 5](#). If the QTc interval on follow-up EKG is ≥ 500 msec, the EKG should be repeated within 7 days and, if the QTc interval remains ≥ 500 msec, the subject should be removed from the study. Additionally, if the QTc interval is increased by 60 msec or more from baseline but the QTc interval remains at <500 msec, the EKG should be repeated within 7 days. If the repeat EKG again shows a ≥ 60 msec increase in the QTc interval from baseline, consideration should be given to removing

the subject from the study or increasing monitoring, after discussion with the principal investigator.

CYP450 Interactions:

In vitro and in vivo animal data indicate that the metabolism of pazopanib is primarily mediated by CYP3A4. In vitro data indicate that pazopanib is a potential inhibitor for CYP2C9, CYP1A2, CYP2A6, CYP2B6, CYP2C8, CYP2C19, CYP2D6, CYP2E1, and CYP3A4. In addition, one in vitro study suggested that pazopanib may induce CYP3A4 at high concentrations. Potent CYP3A4 inhibitors and inducers are prohibited on pazopanib trials. In exceptional circumstances, medications which strongly inhibit CYP3A4 may be administered, with caution, if the dose of pazopanib is decreased to 50% of the dose which would otherwise be administered.

Medications that strongly inhibit CYP3A4 include (but are not limited to):

- Antibiotics: clarithromycin, telithromycin, troleandomycin
- HIV: protease inhibitors (ritonavir, indinavir, saquinavir, nelfinavir, amprenavir, lopinavir)
- Antifungals: itraconazole, ketoconazole, voriconazole
- Antidepressant: nefazodone

Grapefruit juice is also an inhibitor of CYP450 and should not be taken with pazopanib.

Medications that strongly induce CYP3A4 include (but are not limited to):

- Glucocorticoids: cortisone (>50 mg), hydrocortisone (>40 mg), prednisone (>10 mg), methylprednisolone (>8 mg), dexamethasone (>1.5 mg)
- Anticonvulsants: phenytoin, carbamazepine, phenobarbital, oxcarbazepine
- HIV antivirals: efavirenz, nevirapine
- Antibiotics: rifampin (rifampicin), rifabutin, rifapentene
- Miscellaneous: St. John's Wort, modafinil, pioglitazone, troglitazone

Pazopanib is a weak inhibitor of CYP3A4, CYP2C8, and CYP2D6. Drugs that have narrow therapeutic windows and are substrates for these enzymes should be avoided and, if necessary, administered with caution (see [Appendix B](#)). Because of pazopanib's long half-life, caution should continue to be exercised for at least 7 days and up to 15 days after the last dose of pazopanib when administering these medications.

Medications that are substrates for these enzymes *and* have narrow therapeutic windows medications include (but are not limited to):

- Ergot derivatives: dihydroergotamine, ergonovine, ergotamine, methylergonovine (potential increased risk for developing ergot toxicity that includes severe vasospasm leading to peripheral as well as cerebral ischemia)
- Neuroleptics: pimozide (potential increased risk for QT interval prolongation, ventricular arrhythmia, and sudden death)
- Antiarrhythmics: bepridil, flecainide, lidocaine, mexiletine, amiodarone, quinidine, propafenone (potential increased risk for QT interval prolongation and Torsade de Pointes)
- Immune modulators: cyclosporine, tacrolimus, sirolimus (potential increased risk for nephrotoxicity and neurotoxicity)
- Miscellaneous: quetiapine, risperidone, clozapine, atomoxetine

In vitro studies indicate ARQ 197 is metabolized by CYP2C19, and to a lesser extent CYP3A4. The metabolism and consequently overall pharmacokinetics of ARQ 197 could be altered by inhibitors and/or inducers or other substrates of CYP2C19 and CYP3A4. In patients receiving any medications or substances that are inhibitors or inducers of CYP3A4 or CYP2C19, every attempt should be made to change the medications to another agent that does not affect the CYP pathway (see [Appendix B](#)).

Specific recommendations regarding other oral hypoglycemics:

Co-administration of pazopanib with some oral hypoglycemics, including glipizide, glyburide, (glibenclamide), glimepiride, nateglinide, repaglinide, gliclazide, acetohexamide, carbutamide, glibornuride, glymidine, metahexamide, and tolazamide, (but not including tolbutamide and chlorpropamide, which are prohibited) may result in an increase in plasma concentrations of the oral hypoglycemic agents, leading to hypoglycemia. Therefore, reducing the doses of these oral hypoglycemic agents should be considered when pazopanib administration starts. The blood glucose should be monitored closely and patients should be instructed to measure their blood glucose if they experience symptoms of hypoglycemia and inform their physicians if their blood glucose concentrations are low. After at least 14 days of pazopanib administration, the doses of oral hypoglycemic agents may be increased **as necessary** to maintain adequate blood glucose control.

Specific recommendations regarding non-dihydropyridine calcium channel blockers:

Co-administration of pazopanib with calcium channel blockers may result in increased plasma concentrations of the latter. The non-dihydropyridine calcium channel blockers verapamil and diltiazem have potential depressive effects on cardiac conduction and contractility. When pazopanib therapy is initiated, the administration of an anti-hypertensive or anti-anginal agent other than verapamil and diltiazem is recommended in the setting of a PR interval > 200 msec, sinus bradycardia (< 60 beats per minute), or second or third degree heart block, unless the patient has a permanent pacemaker.

5.3.1 Nausea/Vomiting

Anti-emetics will not be administered routinely prior to pazopanib or ARQ 197. However, if a patient develops nausea/vomiting, anti-emetics such as but not limited to prochlorperazine, metoclopramide, 5-HT₃ antagonists, or aprepitant may be given. In addition, if a patient develops nausea and/or vomiting that is Grade 2 or greater, anti-emetics may be instituted prophylactically at the discretion of the investigator. Nausea and vomiting will be considered refractory if it does not resolve to ≤ Grade 1 with treatment with a combination of at least 2 of the antiemetics within 24 hours.

5.3.2 Diarrhea

If diarrhea develops and does not have an identifiable cause other than study drug administration, anti-diarrheals such as Lomotil (diphenoxylate HCl 2.5 mg + atropine sulfate 0.025 mg/tablet) dosed according to package insert or loperamide 4 mg po after the first unformed stool with 2 mg po with every 2 hours (4 mg every 4 hours while asleep), till resolution of episode of at least 12 hours (no more than 16 mg of loperamide

during a 24-hour period). This regimen can be repeated for each diarrheal episode. Diarrhea will be considered refractory if it does not resolve within 24 hours to \leq Grade 2 with the above regimen (maximum of 16 mg of loperamide in a 24-hour period). If the patient develops blood or mucus in the stool, dehydration, or hemodynamic instability, or fever along with the diarrhea, anti-diarrheals will be discontinued and the patient will be treated with IV fluids and antibiotics as medically indicated.

